#### **10.4.2. Phase 2**

Hypothesis for the true response rate will be tested as described below for each cohort independently. With a 1-sided type I error rate of 0.05, each cohort would have 80% power based on true response rate in the alternative hypothesis. Approximately 130 subjects (including 6-9 subjects treated at the RP2D in Phase 1b and with the tumor type as defined for Phase 2) across the three tumor type cohorts will be included in the Phase 2 analyses (an interim analysis and the primary analysis). The Phase 2 statistical design including number of subjects and number of responders for each analysis follows the statistical framework of Simon's optimal two-stage design ([Simon, 1989](#)). The enrollment will continue while the interim analysis is performed.

For each cohort, if a subject discontinues prior to the first tumor response assessment for reasons other than progressive disease, the subject may be replaced.

#### **NSCLC cohort and breast cancer cohort (n=18 for the interim analysis and n=43 for the primary analysis for each cohort):**

For each of the two tumor type cohorts, a true response rate of 10% (H0) versus 25% (Ha) will be tested and the probability of early stopping is at least 73.4% if the true response rate is  $\leq 10\%$  (H0), and no greater than 13.5% if the true response rate is  $\geq 25\%$  (Ha).

An interim analysis will be performed based on the first 18 evaluable subjects (defined in [Section 10.1.2](#)) for each cohort independently. If 2 or fewer responders are observed among the 18 evaluable subjects in a cohort, the enrollment may be stopped. Otherwise, enrollment will continue to enroll an additional 25 evaluable subjects for a total of 43 evaluable subjects for the primary analysis. The null hypothesis will be rejected if 8 or more responders are observed among the 43 evaluable subjects.

For the NSCLC cohort, subjects with adenocarcinoma and squamous-cell carcinoma will be enrolled at an approximate 2:1 ratio (ie, at least 15 subjects with squamous-cell carcinoma will be enrolled).

For the breast cancer cohort, subjects with triple negative or HER2-positive breast cancer will be enrolled at an approximate 2:1 ratio (ie, at least 15 subjects with triple-negative breast cancer will be enrolled).

**Pancreatic cancer cohort (n=17 for the interim analysis and n=44 for the primary analysis):**

A true response rate of 5% (H0) versus 18% (Ha) will be tested and the probability of early stopping is at least 79.2% if the true response rate is  $\leq 5\%$  (H0), and no greater than 16.2% if the true response rate is  $\geq 18\%$  (Ha).

An interim analysis will be performed based on the first 17 evaluable subjects. If 1 or no responder is observed among the 17 evaluable subjects, the enrollment may be stopped.

Otherwise, the enrollment will continue to enroll additional 27 evaluable subjects for a total of 44 evaluable subjects for the primary analysis. The null hypothesis will be rejected if 5 or more responders are observed among the 44 evaluable subjects.

For NSCLC, 10% was chosen based on the fact that, per NCCN guidelines, the reported second- and third-line response rates to systemic chemotherapy have generally been less than 10% and have limited clinical utility. For HER2-positive breast cancer, response rates and PFS in the relapsed setting are low, especially after multiple lines of prior therapy. For third line, published response rates were 22% and 14% in one study ([Geyer 2006](#)). For triple-negative breast cancer, in a Phase 3 study, the response rates were 27% and 9% ([Pivot 2009](#)). In combination with these response rates and given the fact that many of these therapies have intolerable side effects, 10% was chosen for breast cancer overall as the futility endpoint. A 25% response rate would be considered clinically meaningful. For pancreatic cancer, in the relapsed setting, the majority of trials had a response rate below 10% ([Rahma 2013, Walker 2014](#)), and also based on the fact that treatment options are limited for this population, 5% was chosen as the futility endpoint with  $\geq 18\%$  being worth further study.

## **10.5. Subject Information**

The distribution of subjects for each of the analysis populations will be provided. The number of subjects enrolled by each investigative site and country, dosed, and discontinued will be summarized. Treatment discontinuation will be summarized according to the reasons for discontinuation. Demographic and baseline variables will be summarized. Baseline disease characteristics will also be summarized.

## **10.6. Analysis Methods**

Tumor response and disease progression will be based on tumor response assessment per the investigator using RECIST 1.1 guidelines for all three tumor types.

### **10.6.1. Phase 1b Analyses**

The primary objective of Phase 1b is to determine the RP2D or MTD and to evaluate safety and tolerability of ibrutinib in combination with MEDI4736. An algorithm-based 6+3 dose de-escalation design is used to find the RP2D of the combination regimen and to characterize the most frequent adverse events and DLTs. DLTs will be evaluated and will include all AEs

experienced through Phase 1b. Study-drug exposure and laboratory data will be evaluated and summarized by dose cohort and tumor type.

The secondary objectives are to evaluate efficacy and pharmacokinetics / pharmacodynamics in subjects receiving the combination regimen. The ORR along with the corresponding 95% confidence interval based on exact binomial distribution and DOR for responders will be calculated and summarized with descriptive statistics by dose cohort and tumor type. Disease control rate (DCR) at Week 20 (Cycle 5) along with its 95% confidence interval based on exact binomial distribution will be provided by dose cohort and tumor type. Pharmacokinetics and pharmacodynamics data will be summarized by dose cohort and tumor type.

#### **10.6.2. Phase 2 Analyses**

##### Timing of Phase 2 Analysis:

For each tumor type cohort, an interim analysis will be performed to evaluate safety and determine the response rate after the first 18 evaluable subjects for the NSCLC and breast cancer cohorts /17 evaluable subjects for the pancreatic cancer cohort completed at least one tumor response assessment or at least 3 responders in the NSCLC and breast cancer cohorts / 2 responders in the pancreatic cancer cohort were observed, whichever occurs first. Confirmation of response is not required for the interim analysis.

The primary analysis for each cohort will be performed to determine the response rate and safety profile after all subjects included for the Phase 2 analysis have completed at least two tumor response assessments or have progressed prior to the second tumor response assessment. Confirmation of response is required for the primary analysis. A cohort may be discontinued based on the interim efficacy and/or safety results.

The final analysis will be performed at the end of the study (3 years after the first dose of the last subject enrolled) based on all subjects enrolled in this study.

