### 7.2.4. Confirmatory Measurement

#### 7.2.4.1. Confirmation

To be assigned a status of PR or CR as the best overall response, changes in tumor measurements must be confirmed by repeat assessments that should be performed  $\geq 4$  weeks after the criteria for response are first met.

In the case of SD, measurement must have met the SD criteria at least once after study entry at a minimal duration of 6 weeks from Study Day 1.

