1.5.2. Phase 2 Analyses

Interim Analysis for Futility: For each tumor type cohort, the interim analysis will be performed after the first 18 evaluable subjects (for the NSCLC and breast cancer cohorts) / 17 evaluable subjects (for the pancreatic cancer cohort) completed at least one tumor response assessment or at least 3 responders (in the NSCLC and breast cancer cohorts) / 2 responders (in the pancreatic cancer cohort) were observed, whichever occurs first. Confirmation of response is not required for those responders for the interim analysis.

Final Analysis: The final analysis for both safety and efficacy will be performed at the end of the study based on all subjects treated for this study. A Clinical Study Report (CSR) will be produced when the analysis has been performed for all three cohorts.

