1.6. Testing Procedure and Level of Significance

The 2-sided significance level for the final analysis of primary endpoint (ORR) will be 0.05. Analyses of secondary endpoints will be performed using the same significance level.

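### The protocol tests H0 for ORR at a primary analysis and the SAP at end of study, and the protocol's trigger can be met before the last subjects' Week 20 responses can be confirmed

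*Protocol*

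**What the plan says.** **When H0 is tested, protocol.** Section 10.4.2 attaches the rules of at least 8 of 43 (NSCLC, breast) and at least 5 of 44 (pancreatic) to the primary analysis. Section 10.6.2 runs that analysis after all included subjects "have completed at least two tumor response assessments or have progressed prior to the second tumor response assessment"; the synopsis carries the same trigger. A separate final analysis follows 3 years after the last enrolled subject's first dose.

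**When H0 is tested, SAP.** Sections 1.1 and 1.5.2 contain an interim futility analysis and a final analysis, with no primary analysis between them. Section 1.4 attaches the same rules to the final analysis. Section 1.6 does the same for the significance level: "The 2-sided significance level for the final analysis of primary endpoint (ORR) will be 0.05". Section 1.5.2 says the final analysis "will be performed at the end of the study based on all subjects treated for this study". Section 5, which records the major changes from the protocol, does not mention moving the test.

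**What counts as a response.** Protocol 10.6.2 says "Confirmation of response is required for the primary analysis", and 10.6.2.1 counts only confirmed CR or PR. Under 7.2.4.1, tumor changes "must be confirmed by repeat assessments that should be performed" at least 4 weeks after the criteria are first met. Section 7.2 provides for confirmatory scans on the same minimum interval.

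**Scan schedule.** Sections 7.1.3.2.1 and 8.2.2 place scans at the end of Cycle 2 and every third cycle after that.

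**The concern.** The two documents give different answers to a basic question: on which data is H0 accepted or rejected? The cuts are more than two years apart for the last subject, and nothing says which document prevails on this point.

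Within the protocol, the trigger and the endpoint definition also do not fit. The trigger asks for two assessments. A response first seen at the second assessment needs a third before it counts. No section holds the cut for such a response or says how it is counted if still pending.

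The decision turns on a single integer in each cohort, in an open-label trial with investigator-assessed response. An unsettled decision date therefore matters even when few subjects are affected.

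**Working it through.** **1. Calendar for one subject.** With 28-day cycles, the end of Cycle 2 is day 56 (Week 8), of Cycle 5 day 140 (Week 20) and of Cycle 8 day 224 (Week 32), each with a window of -7 days. A response first seen at Week 8 can be confirmed by Week 20 at the latest. One first seen at Week 20 can be confirmed from Week 20 + 4 = Week 24, or at Week 32 if left to the next scheduled scan. The SAP's end-of-study cut, using the protocol's 3 years, is 3 × 52 = Week 156 for the last subject.

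**2. Who is affected.** Only subjects whose Week 20 scan falls within about 4 weeks of the cut, that is, the last enrolled. Those enrolled earlier have had time to confirm.

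**3. The plan's own figures.** Inputs from protocol 10.4.2: "With a 1-sided type I error rate of 0.05, each cohort would have 80% power"; for NSCLC and breast, "a true response rate of 10% (H0) versus 25% (Ha) will be tested"; for pancreatic, "A true response rate of 5% (H0) versus 18% (Ha) will be tested". Write b for the binomial probability, r1 for the largest stage 1 count that stops, and r for the largest total that does not reject.

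P(stop early) = Σ b(x; n1, p) over x = 0 to r1

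P(reject) = Σ b(x; n1, p) × P(Y ≥ r + 1 − x) over x = r1 + 1 to n1, with Y ~ Bin(n − n1, p)

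- NSCLC/breast (r1/n1 = 2/18, r/n = 7/43): early stopping 0.7338 under H0 and 0.1353 under Ha; alpha 0.0480; power 0.8003.
- Pancreatic (1/17, 4/44): early stopping 0.7922 and 0.1621; alpha 0.0469; power 0.8037.

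These reproduce the stated 73.4%/13.5%, 79.2%/16.2%, 80% power and 1-sided 0.05.

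**4. Cost of cutting at the earliest permitted date.** Two assumed quantities are needed: m, the number of late-enrolled stage 2 subjects who cannot yet confirm a Week 20 response, and w, the share of responses first seen at Week 20. Stage 1 stays at the full rate, because the interim does not require confirmation and those subjects have time to confirm later. In stage 2, replace Y by

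Y = Bin(n − n1 − m, p) + Bin(m, p(1 − w)).

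With 4 subjects per month, taking 4 weeks as a month, a 4-week gap gives m = 4. Expected pending responders are m × p × w:

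- NSCLC/breast: 4 × 0.25 × 0.2 = 0.20 to 4 × 0.25 × 0.4 = 0.40
- Pancreatic: 4 × 0.18 × 0.2 = 0.14 to 4 × 0.18 × 0.4 = 0.29

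| Assumed accrual and gap | m | NSCLC/breast power, w = 0.2 to 0.4 | Pancreatic power, w = 0.2 to 0.4 |
|---|---|---|---|
| No subject affected | 0 | 0.800 | 0.804 |
| 2 per month, 4 weeks | 2 | 0.796-0.791 | 0.802-0.799 |
| 4 per month, 4 weeks | 4 | 0.791-0.780 | 0.799-0.795 |
| 8 per month, 4 weeks | 8 | 0.780-0.755 | 0.794-0.783 |
| 4 per month, 12 weeks (confirmation left to Week 32) | 12 | 0.768-0.725 | 0.789-0.769 |

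**5. How close the decision is.** 7/43 = 16.3% does not reject and 8/43 = 18.6% does; 4/44 = 9.1% does not and 5/44 = 11.4% does.

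**6. Type I error if both cuts were tested.** On the same 43 or 44 subjects the count of confirmed responders can only rise between cuts. Rejecting at either cut is therefore the same event as rejecting at the later one, with probability at most 0.0480 or 0.0469 under H0.

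**The case against.** The strongest reply is that the trigger is a floor. It sets a minimum number of assessments, and the protocol states the confirmation requirement alongside it. A sensible team would read the two together and wait. That is a fair reading, and the documents allow it. They do not require it, however, and they do not say what happens to a response still pending at the cut.

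It can also be said that the two defects do not add up. If the SAP governs, the confirmation gap disappears because the test is at end of study. If the protocol governs, there is one test and a small gap. This is right, and the power loss should not be stacked on the conflict over timing.

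Three stronger readings are tempting, and the documents do not support them:

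- **Two looks at H0 with inflated type I error.** Each document contains one H0 test at full sample size. Two arise only by merging them, and step 6 shows no inflation even then.
- **Week 20 responses are counted as non-responses.** No section says so; the text is silent. Only the last-enrolled subjects are exposed.
- **Confirmation waits until Week 32, so power falls to 0.725 or 0.769.** Protocol 7.2 provides for confirmatory scans from 4 weeks after first response, so Week 24 is available. Because no upper limit is set, the longer delay is possible, but it is not the plan.

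**Conclusion.** The conflict over the decision point is established from current text and needs no assumption: the same cut-offs are attached to a primary analysis in the protocol and to an end-of-study analysis in the SAP, and SAP section 5 does not record the difference.

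The confirmation gap is real but narrow. At 4 subjects per month and a 20-40% late-response share, it costs about 1 to 2 percentage points of power in NSCLC and breast and 1 point or less in pancreatic. Both inputs are assumptions. The loss grows with faster accrual or if confirmation is left to Week 32, and vanishes if the sponsor waits. The planned sample sizes and error rates are sound as calculated. What is missing is one defined date for a decision that a single pending response can reverse.

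The difference between the protocol's 1-sided and the SAP's 2-sided level is a separate inconsistency, and this point does not depend on it.

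**What to change.** 1. State in both documents that H0 is tested once per cohort, at the primary analysis.
2. Define its cut in protocol 10.6.2 and the synopsis: every included subject has had the second assessment and, for any response first seen there, the confirmatory assessment at least 4 weeks later, or has progressed, died or left follow-up. This also settles how a pending response is handled.
3. Add this primary analysis to SAP 1.5.2, and attach the cut-offs (SAP 1.4) and the significance level (SAP 1.6) to it.
4. Report end-of-study ORR as an updated estimate without a second test.

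If the sponsor prefers the end-of-study test, amend the protocol to match and list the change in SAP section 5.

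The cost is wording in both documents and a delay of about 4 weeks in the primary cut, or up to 12 if confirmation waits for the next scheduled scan. Sample sizes, cut-offs, alpha (0.0480 and 0.0469) and design power (0.800 and 0.804) do not change.

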##### **10.6.2.1. Primary Efficacy Analysis**

The primary efficacy analysis will be based on ORR using the Response-evaluable Population in each of the three solid tumor cohorts. ORR is the proportion of response-evaluable subjects who achieved a CR or a PR with confirmation. The observed ORR along with its 95% confidence interval based on exact binomial distribution will be calculated and summarized for each tumor cohort.

##### **10.6.2.2. Secondary Efficacy Analyses**

Disease control rate (DCR) at Week 20 (Cycle 5) will be based on the Response-evaluable Population in each of the three solid tumor cohorts. DCR at Week 20 (Cycle 5) is the proportion of response-evaluable subjects who maintain disease control (CR, PR or SD) at Week 20

(Cycle 5). The observed DCR at Week 20 (Cycle 5) along with its 95% confidence interval based on exact binomial distribution will be calculated and summarized for each tumor cohort.

Duration of response (DOR) is defined as duration of time from the date of initial response to the date of disease progression or the date of death due to any cause, whichever occurs first, and will be calculated and summarized with descriptive statistics for responders by tumor type cohort. The Kaplan-Meier estimate will be provided for DOR, if a sufficient number of responders are observed; censoring conventions for DOR will be provided in the SAP.

Progression-free survival (PFS) and OS will be evaluated by tumor type cohort with Kaplan-Meier estimates using the Safety Population. PFS is defined as duration of time from the first dose date of study drug (ibrutinib or MEDI4736) to the first documentation of disease progression per investigator using RECIST 1.1 guidelines or the date of death due to any cause, whichever occurs first. OS is defined as duration of time from the first dose date of study drug (ibrutinib or MEDI4736) to the date of death due to any cause. Censoring conventions for those two endpoints will be described in the statistical analysis plan (SAP).

Pharmacokinetics and pharmacodynamics profiles will be evaluated by tumor type cohort and overall.

#### **10.6.2.3. Exploratory Efficacy Analyses**

**Subgroup Analyses:** For each tumor type cohort, a subgroup analysis will be conducted to calculate response rate and its 95% confidence interval based on PD-L1 expression (positive versus negative). For the NSCLC cohort, a subgroup analysis will also be conducted based on subjects with adenocarcinoma versus squamous-cell carcinoma. For the breast cancer cohort, a subgroup analysis will also be conducted based on subjects with HER2-positive versus triple-negative breast cancer.

**Other analyses:** Other exploratory efficacy variables will be summarized descriptively and may include the following:

- Immune cell subsets
- Non-BTK-related pharmacodynamics (ie, EGFR, ITK)
- Plasma chemokine/cytokine levels
- Genes and/or proteins (within the tumor or other collected specimens) associated with sensitivity or resistance to ibrutinib

#### **10.7. Safety Analysis**

Analysis of safety data will be conducted on the safety population, which includes enrolled subjects who received at least one dose of study drug. The baseline value is defined as the last value collected on or prior to the first dose date of study drug (ibrutinib or MEDI4736, whichever comes first).

The safety variables to be analyzed include exposure of study drug, AEs, clinical laboratory test results (hematology and chemistry), ECOG performance, physical examination and vital sign measurements. Exposure of study treatment and reasons for discontinuation from study treatment will be tabulated. In general, continuous variables will be summarized using descriptive statistics (n, mean, median, standard deviation, standard error and range). Categorical variables will be summarized using frequencies and percentages. No formal statistical testing is planned.

#### **10.7.1. Adverse Events**

Adverse event parameters to be evaluated are the type, incidence, and intensity of adverse events; the relationship of adverse events to study treatment; and the action taken with respect to study treatment due to adverse events.

The verbatim terms used in the eCRF by Investigators to identify adverse events will be coded using the Medical Dictionary for Regulatory Activities (MedDRA). Treatment-emergent AEs will be defined in the statistical analysis plan.

All treatment-emergent AEs will be included in the analysis. For each AE, the number and percentage of subjects who experience at least one occurrence of the given event will be summarized. The number and percent of subjects with treatment-emergent adverse events will be summarized according to intensity ([CTCAE, v4.03](#)) and drug relationship, as well as categorized by system organ class and preferred term. Summaries, listings, datasets, or subject narratives may be provided, as appropriate, for those subjects who die, who discontinue treatment due to an AE, or who experience an SAE.

#### **10.7.2. Clinical Laboratory Tests**

Laboratory tests will be summarized separately for hematology and serum chemistry. Local laboratory results will be converted based on the normal ranges and standardized using the International System (SI) unit. Selected hematology and chemistry laboratory parameters are detailed in [Section 7.1.2](#). Laboratory values will be graded using the [CTCAE v4.03](#).

Descriptive statistics will be provided for the values of selected clinical laboratory tests at each scheduled on-treatment evaluation including the final value. Percent change from baseline to each scheduled on-treatment evaluation and to the final value will also be summarized.

For selected variables, the mean value and mean percent change over time will be presented graphically.

A summary of the shifts in selected laboratory hematology and serum chemistry parameters from baseline to the worst toxicity grade during the study will be provided. The worst toxicity grade during the study will be tabulated.

## 10.8. Dose Level Review Committee

A Dose Level Review Committee will be established to evaluate the safety data from each cohort of the Phase 1b on an ongoing basis. Members of this committee will include participating investigators or designees as well as the Sponsor (the Medical Monitor or designee, a Drug Safety representative, and a statistician at a minimum).

## 10.9. Pharmacokinetic Analysis (Ibrutinib, Combination of Ibrutinib and MEDI4736)

Ibrutinib and PCI-45227 bioanalytical data will be used in noncompartmental pharmacokinetics analysis. Plasma concentrations below the lowest quantifiable concentration will be treated as zero in the summary statistics. All subjects and samples excluded from the analysis will be clearly documented in the pharmacokinetics summary.

Descriptive statistics will be used to summarize ibrutinib and PCI-45227 concentrations at each sampling time point and pharmacokinetics parameters of ibrutinib and PCI-45227 (including but not limited to:  $C_{max}$ ,  $T_{max}$ ,  $AUC_{last}$ , and  $t_{1/2}$ ).

Mean plasma ibrutinib and PCI-45227 concentration time profiles will be plotted.

Ibrutinib data from this study may also be combined with data from other studies performed with ibrutinib in subjects with hematologic malignancies as part of a population-pharmacokinetics analysis using nonlinear mixed effects models. For the population-pharmacokinetics analysis, covariates that could potentially correlate with plasma pharmacokinetics parameters will be evaluated. The results of the population-pharmacokinetics analyses (if performed) will be presented in a separate report.

For the drug combination of ibrutinib and MEDI4736, model-derived exposure parameters (PK parameters) may be used to explore PK/PD correlation between the exposure of ibrutinib and its active metabolites with relevant clinical or biomarker information to assess effectiveness and toxicity.

Ibrutinib and MEDI4736 PK data in this study will be compared to observed/reported concentration data for ibrutinib and MEDI4736 and/or concentration estimates from the existing literature and/or population PK models to explore the potential for a pharmacokinetic interaction between ibrutinib and MEDI4736.

